**12- Data Sources / Measurements:**

[figure not shown]
- Retrospective Data Analysis will be performed after the CBCT images are pooled from the computer database.
- Exposure parameters of the scans were as following; scanned using Cranex® 3DX SOREDEX, 0.2 voxel resolution, 8 × 6 cm FOV, 90 kVp, 10 mA and 6 seconds exposure time
- CBCT images will be analysed using OnDemand3D ® App (Cybermed, Seoul, Korea); using the 3D module, reference lines are modified to confine with the buccolingual orientation of the inferior alveolar loop, to obtain a modified axial cut showing the inferior alveolar loop and mental foramen opening on the same plane.

In scans with an anterior loop, on the corrected axial cut the distance between the most mesial point of the mental foramen and the maximum mesial extension of the anterior loop will be measured *Von Arx et al 2013* (Figure 3).

**Figure 3:** the distance between the most mesial point of the mental foramen and the maximum mesial extension of the anterior loop will be measured *Von Arx et al 2013*

- Using the DVR module; an arch line will be drawn on the axial plane to obtain a reformatted panorama; then the mesial extension of the AL will be detected and its length will be measured by counting the number of the consecutive adjacent vertical cuts on cross-sectional view between the slice showing the anterior border of the mental foramen and the anterior border of the loop using slice interval of 1mm *Apostolakis et al 2012* (Figure 4).

**Figure 4:** Cross-sectional reconstructions showing the AL *Apostolakis et al 2012*

- CBCT images will be interpreted by two oral radiologists independently; blinded from demographic data of the patients and from the results of each other.
- Each radiologist will evaluate the images for detection of the anterior loop and measuring its length. Then one of them will re-evaluate the images with two weeks interval between the two reading sessions.
- Intra-observer and inter-observer and variability between the observers will be evaluated.

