### **PO question**

**P:** mandible quadrants in Adult Egyptian Population.

**O:** Presence of the anterior loop of the inferior alveolar nerve; and its length in the mandibles of adult Egyptian population

	Outcome Measured	Measuring Device	Measuring Unit
Primary Outcome	Prevalence of the anterior loop	CBCT axial cuts (Ondemand 3D software)	Categorical nominal data Percentage (%)
Secondary Outcomes	length of the anterior loop	Built in measuring tools (axial cuts) in Ondemand 3D software “MPR* module”	mm
	Mesial extension of the anterior loop	Cross-sectional cuts on Ondemand 3D software “DVR** module”	mm

\* MPR: Multiplanar Reformatting

\*\* DVR: Direct Volume Rendering

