### **Research question:**

How frequent is the anterior loop and how long its mesial extension is in a sample of Egyptian population?

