**11- Details about variable**

1. Length of anterior loop's mesial extension if present.
2. Sex of the patient will be identified and addressed as the prevalence of the anterior loop of the IAN and its length may show sex predilection.

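### Minor: mesial extension is counted in 1 mm cuts on scans with 0.2 voxels; a finer interval on the same stored images would cheaply remove most of the rounding, though landmark error would remain

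*Combined protocol and SAP*

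**What the plan says.** The PO question table lists two secondary lengths in mm: the length of the loop, taken with the measuring tools on axial cuts, and its mesial extension, taken on "Cross-sectional cuts on Ondemand 3D software". The research question asks "how long its mesial extension is", and section 11 names as its first variable the length of the loop's "mesial extension if present".

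Section 12 gives the methods. The scans have "0.2 voxel resolution". For the first length, the plan measures directly "on the corrected axial cut the distance between the most mesial point of the mental foramen" to the furthest mesial reach of the loop. For the second, "an arch line will be drawn on the axial plane to obtain a reformatted panorama", and the reader then counts adjacent vertical cuts between the "anterior border of the mental foramen and the anterior border of the loop using slice interval of 1mm". The 1 mm interval is supported by a citation and not discussed further.

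Two radiologists read independently and one reads again after two weeks, giving three readings. The same section adds: "Intra-observer and inter-observer and variability between the observers will be evaluated". Section 16 summarises numerical data as mean and SD or median and range.

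**The concern.** A count of 1 mm cuts can only return whole millimetres, although the stored data are about five times finer. The prevalence estimate does not use the count. What is exposed is the individual values of mesial extension, their reported spread, and reader agreement. Two readers who place a border a fraction of a millimetre apart can be recorded as a full millimetre apart, so part of the reported disagreement would reflect a software setting and not the readers. Values recorded only at 1 mm cannot be refined later without reading the scans again.

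**Working it through.** **Inputs from the plan.** Interval h = 1 mm and voxel 0.2 (unit not stated; mm assumed), section 12. Planning prevalence 24.3% and 192 subjects, section 14; 192 quadrants, section B. The plan states no measurement error, no SD of length and no agreement target, so there is no figure of its own to reproduce on this point.

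**Assumptions.** Localisation error per border, SD c = 0.2, 0.3 or 0.5 mm. True SD of length 1, 1.5 or 2 mm. Two cases for cut placement, because section 12 does not say which applies: the first cut anchored on the foramen border (one end rounded), or placed at random (both ends rounded).

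**Step 1: rounding alone.** SD = h/√12 (anchored) or h/√6 (random).

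| Interval | Anchored | Random |
|---|---|---|
| 1 mm | 0.289 mm | 0.408 mm |
| 0.5 mm | 0.144 mm | 0.204 mm |
| 0.2 mm | 0.058 mm | 0.082 mm |

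Simulating the count, with true lengths uniform on 0.5 to 6.5 mm, gives the same values at 1 mm and 0.2 mm.

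**Step 2: total error per loop.** Total SD = √(h²/12 + 2c²) anchored, or √(h²/6 + 2c²) random. Example (anchored, c = 0.2): √(0.0833 + 0.08) = 0.404 mm at 1 mm, and √(0.0033 + 0.08) = 0.289 mm at 0.2 mm. The fall is 1 − 0.289/0.404 = 28.6% from unrounded values.

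| c per border | Anchored, 1 vs 0.2 mm | Fall | Random, 1 vs 0.2 mm | Fall |
|---|---|---|---|---|
| 0.2 mm | 0.404 vs 0.289 | 29% | 0.497 vs 0.294 | 41% |
| 0.3 mm | 0.513 vs 0.428 | 17% | 0.589 vs 0.432 | 27% |
| 0.5 mm | 0.764 vs 0.709 | 7% | 0.816 vs 0.712 | 13% |

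**Step 3: limits of agreement between two readers** (±1.96 × SD of the simulated difference, in mm, 1 mm vs 0.2 mm).

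| c per border | Anchored | Random, shared arch line | Random, separate arch lines |
|---|---|---|---|
| 0 | 0 vs 0 | 0 vs 0 | ±1.13 vs ±0.23 |
| 0.2 mm | ±1.11 vs ±0.80 | ±1.32 vs ±0.82 | ±1.38 vs ±0.82 |
| 0.5 mm | ±2.12 vs ±1.97 | ±2.26 vs ±1.97 | ±2.26 vs ±1.97 |

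With perfect localisation, rounding affects agreement only if arch lines are separate and cut placement is random. Otherwise both readers round the same length in the same way.

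**Step 4: reported mean and SD.** Expected loops: 192 × 0.243 = 46.7. The 95% half-width of the mean is 1.96 × √(SD² + rounding variance)/√46.7.

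- True SD 1 mm: 0.299 (anchored) or 0.310 (random) at 1 mm, against 0.287 or 0.288 at 0.2 mm.
- True SD 1.5 mm: 0.438 or 0.446, against 0.431.
- True SD 2 mm: 0.580 or 0.586, against 0.574.

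The change is about 0.01 to 0.02 mm. Inflation of the reported SD at 1 mm, √(1 + e²/SD²) − 1 with e the rounding SD, is 4% (anchored) or 8% (random) for a true SD of 1 mm, and 1% or 2% for 2 mm.

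**The case against.** The best defence has three parts.

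- **The 1 mm count follows a published method,** and keeping it for comparability is reasonable. This stands as a reason to retain a 1 mm count. It is not a reason to record nothing finer, since the coarse count can be taken from the fine cuts.
- **The axial-cut distance is close to the same anatomical quantity and is not rounded to 1 mm.** Section 15 reports the length of the loop as mean and SD, which may already mean that measure. This stands in part. However, the PO question table lists mesial extension as a separate outcome with its own method, so the axial length does not repair it.
- **Nothing inferential changes.** This stands in full: prevalence is untouched, the mean barely moves, and the plan sets no precision or agreement target for length.

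A reader might also infer three stronger things that the documents do not support.

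- **A five-fold fall in measurement error.** That ratio belongs to the rounding component alone; border localisation is unchanged, and the plan gives no figure for it.
- **Rounding passes fully into reader disagreement whenever each reader draws an arch line.** This also needs random cut placement. With the first cut anchored and perfect localisation, the limits are zero at either interval.
- **The mean is biased.** Anchoring and counting only complete intervals would shift it by −0.5 mm (−0.1 mm at 0.2 mm), but the counting rule may be shown in Figure 4, which is not available here. That is a matter for clarification, not an error.

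**Conclusion.** The point holds as a minor, inexpensive improvement to one secondary outcome. The 1 mm count adds a rounding SD of 0.29 to 0.41 mm per loop, where 0.06 to 0.08 mm is attainable if the voxel size is 0.2 mm and the software can cut that finely. The benefit in total error ranges from about 41% down to 7%, depending on cut placement, which the plan does not state, and on localisation error, which is assumed here at 0.2 to 0.5 mm per border. The gain is worth having if readers locate borders well and slight if they do not. It bears on individual values, spread and agreement; the study's conclusions do not rest on it.

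**What to change.** In section 12:

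1. Set the cross-sectional interval to the voxel size, or the finest the DVR module allows. An interval of 0.5 mm already halves the rounding component.
2. Define mesial extension as (slice index of the loop's anterior border − slice index of the foramen's anterior border) × interval. This also settles how end slices are treated.
3. If 0.2 mm is used, also count every fifth cut under the cited method's own rule, for comparison with published 1 mm counts. Rounding the fine value is not a substitute: with random placement it gives an error SD of 0.294 mm, against 0.408 mm for a true 1 mm count.
4. State whether each reading draws its own arch line and how the first cut is placed.
5. If the interval cannot be changed, use the axial-cut distance already planned for the reported SD and agreement of length.

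**Cost.** One setting and a few sentences; the scans are stored, so no new imaging or readers are needed. The downside is about five times as many cuts to scroll: a 3 mm loop spans 15 cuts instead of 3. If 192 means quadrants, that applies to 192 × 0.243 ≈ 47 loops, or 140 readings over three sessions. If it means subjects with both sides imaged, it is 384 × 0.243 ≈ 93 loops, or 280 readings. Both counts assume that the planning prevalence applies per quadrant. The documents do not say which intervals the module offers, hence item 5.

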### **13- Addressing potential sources of bias:**

No source of bias. CBCT images will be interpreted by two oral and maxillofacial radiologists independently blinded from demographic data of the patients and from the results of each other.

D) Study Size:

### **14- Study Size:**

The aim of this study is to detect the prevalence and length of the anterior loop among a sample of Egyptian population. Based upon the results of *Shariati et al 2017*, the prevalence of the anterior loop= 24.3%. Using alpha ( $\alpha$ ) level of (5%), acceptable margin of error = 6%, the minimum estimated sample size was 192 subjects. Sample size calculation was performed using Epi Info 7.2.2.2

E) Quantitative variables

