### **B) Participants:**

Based on sample size calculation, a sample of 192 CBCT images of mandible quadrants belonging to Egyptian individuals will be examined. The selection of the scans to be included will be based on the following eligibility criteria.

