### **16- Statistical methods:**

Data will be analyzed using IBM SPSS advanced statistics (**Statistical Package for Social Sciences**), version 21 (**SPSS Inc., Chicago, IL**). Numerical data will be described as mean and standard deviation or median and range. Categorical data will be described as numbers and percentages. A p-value less than or equal to 0.05 will be considered statistically significant. All tests will be two tailed.

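### Section 14 sizes the study at 192 independent subjects but the Participants section spends the 192 on mandible quadrants, so the 6% margin fails if patients contribute both sides

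*Combined protocol and SAP*

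**What the plan says.** The protocol's only precision statement is in Section 14 (Study Size). It takes from an earlier study that "the prevalence of the anterior loop= 24.3"%, uses a 5% alpha level, and concludes: "acceptable margin of error = 6%, the minimum estimated sample size was 192 subjects". It names the software ("Sample size calculation was performed using Epi Info 7.2.2.2") but not the formula, and it gives no population size.

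Section B (Participants) says its figure rests on that calculation, but the unit has changed: "a sample of 192 CBCT images of mandible quadrants belonging to Egyptian individuals will be examined". The PO question also names mandible quadrants as the population. Section 15 counts CBCT scans of individuals in whom a loop is seen, which is a third unit.

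The inclusion criteria in Section 9 accept scans covering one side or both sides of the anterior mandible. No rule limits a patient to one quadrant. Section 16 (Statistical methods) lists descriptive summaries, a significance threshold and two-tailed testing. It gives no confidence-interval method for the prevalence and nothing on two quadrants from the same patient.

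**The concern.** A margin from a single-proportion formula holds when each unit adds independent information. The left and right quadrants of one mandible share a patient, so the presence of a loop on one side may well be associated with its presence on the other. With positive correlation, 192 quadrants carry less information than 192 patients, and the interval around the prevalence is wider than Section 14 leads the reader to expect.

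The precision of the primary estimate is at stake. Prevalence is the primary outcome, and the 6% margin is the only design justification offered. As written, 192 could mean anything from 96 patients (all contributing both sides) to 192 patients (each contributing one). A reader cannot tell which, and so cannot tell what precision was planned. An interval computed at the end as if the quadrants were independent would carry the same fault into the results.

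**Working it through.** **Inputs**
- Anticipated prevalence p = 0.243, level 5%, margin d = 0.06, n = 192: all from Section 14.
- z = 1.96. Section 16 states two-sidedness for tests ("All tests will be two tailed"). I assume the margin is likewise the half-width of a two-sided 95% interval.
- Within-patient correlation ρ: not in the documents. I use 0.3, 0.5 and 0.7 as an assumed range.
- Share f of the quadrants that come from patients contributing both sides: not in the documents. It can run from 0 to 1.

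**Step 1: the plan's own figure**

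n = z² p(1 − p) / d² = 1.96² × 0.243 × 0.757 / 0.06² = 196.3, rounded up to 197.

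Half-width at 192 independent units = 1.96 × √(0.243 × 0.757 / 192) = 6.07 points. At 197 it is 5.99 points.

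So 192 is within 5 units of the simple formula. To the whole percentage point in which the protocol states its margin, 192 gives 6%.

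**Step 2: effect of pairing**

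If a share f of the quadrants belongs to two-sided patients, the variance of the estimated prevalence is multiplied by the design effect 1 + fρ. The half-width is then 6.07 × √(1 + fρ).

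| Composition of the 192 quadrants | Patients | ρ = 0.3 | ρ = 0.5 | ρ = 0.7 |
|---|---|---|---|---|
| All from different patients (f = 0) | 192 | 6.1 | 6.1 | 6.1 |
| Half from two-sided patients (f = 0.5) | 48 + 96 = 144 | 6.5 | 6.8 | 7.0 |
| All paired (f = 1) | 96 | 6.9 | 7.4 | 7.9 |

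For the last row, the design effects are 1.3, 1.5 and 1.7; for example, 6.07 × √1.5 = 7.4.

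**Step 3: would the simple-formula sample size solve it?**

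No. With 197 quadrants, all paired, and ρ = 0.5, the half-width is 5.99 × √1.5 = 7.3 points, against 7.4 with 192. To restore 6 points with all quadrants paired, the simple formula would need 196.3 × 1.3, × 1.5 or × 1.7, which is about 256, 295 or 334 quadrants. The unit drives the result, not the five-unit difference.

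**Step 4: routes to 192**
- A finite-population correction, n₀ / (1 + n₀/N) with n₀ = 196.3, gives 191.6 at N = 8,000, 192.0 at N = 8,700 and 192.5 at N = 10,000. These population sizes are assumptions.
- Subtracting z² from 196.3 (an Agresti-Coull type adjustment) gives 192.4.
- The Wilson half-width at 192 is 6.03 points.

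The protocol does not say which route, if any, was taken.

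**The case against.** The strongest defence is that the widened margins rest on assumptions. The documents give no within-patient correlation, and having every patient contribute both sides is the extreme case. Section 9 explicitly allows one-sided scans, so 96 fully paired patients is not the stated plan. This is also a descriptive study with no power requirement or decision threshold, and the interval finally obtained will depend on the prevalence observed. All of this is fair. It is why the result is given as a range and the fully paired figures as an upper case for each correlation. It does not remove the conflict: Section 14 counts subjects, Section B counts quadrants on the strength of the same calculation, and nothing prevents or adjusts for two quadrants per patient.

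A reader might also infer a stronger charge: that 192 is an arithmetic error and should read 197. The documents do not support that. The simple formula does give 197, but Section 14 does not say that this formula was used. A finite-population correction with N near 8,700 would give 192. That is conceivable, since Section 8 draws the scans from one centre's database, although its size is not stated. At 192 the half-width is 6.07 points, which rounds to the stated 6%. The calculation is incompletely documented; it is not shown to be wrong.

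**Conclusion.** The point holds as a conflict over the unit of analysis. The 6% margin in Section 14 applies to 192 independent units. The 192 quadrants in Section B need not be independent, and where patients contribute both sides with positive correlation the stated margin is too favourable.

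If all quadrants are paired, the half-width is about 6.9 to 7.9 points for assumed correlations of 0.3 to 0.7, or roughly 1 to 2 points above the stated 6. With a mixture of one-sided and two-sided scans it lies between about 6.1 and those values. The figures assume the 24.3% planning prevalence and a normal-approximation interval. Neither the correlation nor the share of two-sided scans is given, so the exact widening cannot be stated.

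The difference between 192 and 197 is a minor documentation note. On its own it moves the margin by 0.07 points and is not a material error.

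**What to change.** Make Section B, Section 14 and Section 15 use one unit, in one of two ways.

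1. **Count patients.** Recruit 192 patients, and say how a patient is classified: one quadrant per patient chosen by a stated rule, or loop present on at least one side. The second definition is a different prevalence from the per-quadrant one, and a one-sided scan cannot fully determine it. Check that the 24.3% planning figure refers to the same unit.
2. **Keep 192 quadrants.** Restate the margin in Section 14 with the design effect, giving the assumed correlation and the expected share of two-sided scans. In Section 16, specify a confidence interval for prevalence that allows for two quadrants per patient, such as a cluster-robust interval or generalised estimating equations with patient as the cluster. Report the number of patients beside the number of quadrants.

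In the same edit to Section 14, state the formula and any population size entered in Epi Info, or give the margin for 192 independent units as 6.1%.

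Option 2 costs a few sentences, a patient identifier in the data set and a less favourable stated margin; it needs no extra scans. Option 1 may mean retrieving scans from up to 96 more patients than a fully paired sample would use, all from the existing database.

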### **15- Handling of quantitative variables in analyses:**

The number of CBCT scans of Egyptian individuals with an anterior loop of the IAN will be counted and its length will be measured to estimate the variations in the Egyptian population. The length of the anterior loop will be handled as mean and standard deviation.

F) Statistical methods:

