### **9- Eligibility criteria and selection method:**

#### **✓ Inclusion criteria:**

- CBCT scans of adult Egyptian patients, males and females.
- CBCT scans with unilateral or bilateral anterior mandibles; with minimum 2 mm length distal to the mental foramen (mental foramen & anterior mandible are clearly delineated)

*Moghddam et al, 2017.*

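### The unit of the primary prevalence is not consistent: section 15 counts scans with a loop, while the declared population is mandible quadrants and a scan may contain two

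*Combined protocol and SAP*

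**What the plan says.** The combined protocol and SAP names the unit of the primary outcome in several ways.

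- **PO question, population line:** "mandible quadrants in Adult Egyptian Population". The outcome line just below speaks instead of the loop and "its length in the mandibles of adult Egyptian population".
- **B) Participants:** "a sample of 192 CBCT images of mandible quadrants belonging to Egyptian individuals will be examined".
- **Section 9, inclusion criteria:** "CBCT scans with unilateral or bilateral anterior mandibles" are eligible, so one scan may show one side or two.
- **Section 14, Study Size:** "the minimum estimated sample size was 192 subjects". The input is "the prevalence of the anterior loop= 24.3" percent, with no statement of whether this is per side or per patient.
- **Section 15:** "The number of CBCT scans of Egyptian individuals with an anterior loop of the IAN will be counted".

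Section 16 says only that categorical data will be given as numbers and percentages. Section 12 describes measuring the loop in scans that have one, but not how two sides of the same scan are recorded. No section states the denominator of the prevalence or a counting rule for bilateral scans.

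**The concern.** The study is descriptive and its primary result is one percentage, so numerator and denominator must be in the same unit, and that unit must be the one the question names. On its plain wording, section 15 gives a bilateral scan with two loops the same weight as a scan with one. That count is not the number of quadrants with a loop.

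The same readings could then yield quite different headline figures according to what the count is divided by, and a reader could not tell whether the result is a risk per side or per patient. Comparison with published figures would be unsafe for the same reason.

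**Working it through.** **The plan's own figure.** Inputs from section 14: p = 0.243, margin d = 0.06, alpha 5% taken as two-sided (z = 1.96). The single-proportion formula gives n = z²p(1−p)/d² = 1.96² × 0.183951 / 0.0036 = 196.3, or 197 after rounding up. The stated 192 is within 3% of this. A finite population correction with a population near 9,000 would give about 192, but no population size is stated. The half-width at n = 192 is 1.96 × √(0.183951/192) = 6.07 points. So the 192 is broadly reproduced. The formula does not show whether it counts subjects or quadrants; 192 subjects could supply anything from 192 to 2 × 192 = 384 quadrants.

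**Effect of counting scans.** Three quantities are not in the documents and are assumed:

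- 24.3% is a per-quadrant prevalence.
- The share f of the 192 quadrants that come from bilateral scans is 0, 0.5 or 1.
- The correlation ρ between the two sides of one patient is 0, 0.5 or 1.

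For a bilateral scan:

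- P(both sides) = p² + ρp(1−p) = 0.059049 + ρ × 0.183951
- P(any side) = 2p − P(both) = 0.486 − P(both)

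This gives P(any side) = 0.427, 0.335 and 0.243 for ρ = 0, 0.5 and 1.

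The number of bilateral scans is 192f/2 and of unilateral scans 192(1−f). Expected scans with a loop = (192f/2) × P(any) + 192(1−f) × 0.243. For f = 1 and ρ = 0.5 this is 96 × 0.335 = 32.2 scans, against 192 × 0.243 = 46.7 quadrants with a loop.

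| Share of quadrants from bilateral scans | ρ | Scans with a loop | Divided by 192 quadrants | Divided by number of scans |
|---|---|---|---|---|
| 0 (192 scans) | any | 46.7 | 24.3% | 24.3% |
| 0.5 (144 scans) | 0 | 43.8 | 22.8% | 30.4% |
| 0.5 | 0.5 | 39.4 | 20.5% | 27.4% |
| 0.5 | 1 | 35.0 | 18.2% | 24.3% |
| 1 (96 scans) | 0 | 41.0 | 21.3% | 42.7% |
| 1 | 0.5 | 32.2 | 16.7% | 33.5% |
| 1 | 1 | 23.3 | 12.2% | 24.3% |

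Quadrants with a loop divided by quadrants examined gives 24.3% in every row.

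Against the plan's 6-point margin: with all scans bilateral and ρ = 0.5, scans over quadrants falls 24.3 − 16.7 = 7.6 points short, and scans over scans lies 33.5 − 24.3 = 9.2 points above. With half the quadrants from bilateral scans and ρ = 0.5, the differences are 24.3 − 20.5 = 3.8 points down and 27.4 − 24.3 = 3.1 points up, both inside the margin.

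**The case against.** A reader might infer that the plan divides loop-positive scans by 192 quadrants and so is bound to understate the prevalence. The documents do not support that. Section 15 gives a count without a denominator, and no other section divides it by quadrants. Section 14 speaks of subjects; if the count is set against subjects or scans, the result is an any-side figure at or above the per-quadrant one. If all scans are unilateral, there is no bias at all.

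The word scan may also be loose. The Participants section first describes images of quadrants and in its next sentence calls the items to be selected scans. Read that way in section 15, both numerator and denominator are quadrants and nothing is lost. Section 15 is, besides, headed as dealing with quantitative variables, while the primary outcome is categorical.

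These arguments dispose of a definite downward bias. They do not settle the unit. Section 9 uses scan for something that may hold two sides, and section 15 ties its scans to individuals, so counting a bilateral scan once is the natural reading. Section 16 gives no alternative rule. Scans over scans does not rescue the plan either: in a mix of unilateral and bilateral scans it is neither a per-quadrant prevalence nor a clean per-patient one, because patients imaged on one side can be found positive on that side only.

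**Conclusion.** The point holds as an inconsistency of unit whose direction is conditional. Quadrants, subjects and scans of individuals are all used for the same primary outcome, bilateral scans are eligible, and the one stated count records a scan with two loops once. That count does not in general estimate the prevalence in the declared population of quadrants.

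With 24.3% taken as the per-quadrant prevalence, and f and ρ each ranging from 0 to 1, the reported figure would lie between 12.2% and 24.3% if divided by quadrants and between 24.3% and 42.7% if divided by scans. These are illustrations: the documents give neither the bilateral share nor the between-side correlation. The stated count recovers the per-quadrant figure when no scan is bilateral, and scans over scans also does so when the two sides always agree. Departures beyond the 6-point margin need a substantial share of bilateral scans. This should be corrected before the counts are made, because it concerns a stated rule for the primary result.

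**What to change.** In section 15, replace the count of scans with: *the number of mandible quadrants with an anterior loop divided by the number of quadrants examined*. Make the unit attached to the 192 in section 14 agree with the Participants section.

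Optionally, add a separately labelled result among patients with both sides imaged: the percentage with a loop on no side, one side and both sides, with patients as the denominator. This is not needed to cure the inconsistency.

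The cost is one sentence in section 15, one word or phrase in section 14 and, if wanted, one small table. No new scans or readings are required. If the investigators already meant to count quadrants, the change only records that.
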